5.2.2 Cell-free DNA (cfDNA), circulating tumor DNA (ctDNA) and plasma banking

- Collect 10 mL of blood in one cell-free DNA (e.g., Streck BCT/collection tubes) and 10 mL of blood in one K2EDTA tube; gently invert the tubes 8-10 times immediately after collection.
- Labels listing the patient's name, date of birth, date and time of the blood draw will be affixed to all the tubes by the staff person who obtained the samples. Plasma will be isolated and frozen at -80°C until analysis (e.g., centrifuged at 1800 x g for 10 minutes at room temperature; plasma transferred/frozen in aliquots of 1.5-2 mL each).
- Lymphoid Malignancies Branch Clinical Research personnel will arrange for these samples to be delivered to Clinical Support Laboratory, Leidos Biomedical Research, Inc.in Frederick, MD for sample processing per established techniques maintained within standard operating procedures in the laboratory.

5.2.3 Peripheral blood mononuclear cell (PBMC) banking

- Collect blood in 10 mL Na-heparin (green-top) tubes; gently invert tubes 8-10 times immediately after collection.
- Labels listing the patient's name, date of birth, date and time of the blood draw will be affixed to all the tubes by the staff person who obtained the samples. Peripheral blood mononuclear cells (PBMCs) will be isolated by Ficoll-High-Paque Density Gradient Centrifugation and frozen at -20°C or lower until analysis.
- Lymphoid Malignancies Branch Clinical Research personnel will arrange for these samples to be delivered to Clinical Support Laboratory, Leidos Biomedical Research, Inc.in Frederick, MD for sample processing per established techniques maintained within standard operating procedures in the laboratory.

5.3 TISSUE SAMPLES

5.3.1 Immunohistochemistry (IHC)

- Archival block(s) or slides (i.e., at least 15 unstained slides, 5-microns) are required at baseline for participants if there are no circulating lymphoma cells or if the amount of circulating leukemia/lymphoma cells is insufficient to perform the correlative studies. Patients with prior skin, lymph node, or visceral biopsies performed at NIH or outside institutions must make specimen blocks available to the NCI Pathology Department for analysis. If no prior biopsies are available at the time of screening, patients with Cutaneous T-cell lymphoma and other lymphoma with skin involvement will undergo a punch biopsy of a skin lesion, performed by an NIH Clinical Center dermatologist. Patients with lymph node and/or visceral involvement will undergo an 18g core biopsy performed by the

Department of Radiology and Imaging Sciences' Interventional Radiologists (IR). An optional biopsy will be performed in the same manner at timepoints listed in **5.1.1**.

- Prior specimen blocks will be sent to NCI Pathology Department via FedEx. For patients with no prior samples who undergo biopsy as part of screening (if needed for diagnosis) or baseline, core tumor tissue (or bone marrow aspirate/biopsy) samples will be collected and placed in appropriate media (e.g., RPMI 1640 with 10% human serum and antibiotics, and formalin) and processed per established techniques. As indicated (Sections **5.1** and **5.2**), samples will be sent to the Department of Laboratory Medicine (DLM)/ NCI Laboratory of Pathology (LP) for concurrent routine histologic analysis and reporting and IHC testing and tumor-associated immune cells in addition to research testing (i.e., storage for subsequent single-cell analyses).

5.4 OTHER SAMPLES

5.4.1 Germline DNA

- Germline DNA will be collected by blood, buccal swab, and/or saliva samples (preferred). These will ideally be collected at baseline; however, may be collected at any point on study based on supplies. Standardized, commercial collection kits or tubes will be used (e.g., 1, 5-10 mL K₂EDTA tube for blood; Isohelix SK-1 for buccal swabs; Salviette/Oragene® for saliva). In the case of buccal swabs, two (2) samples may be collected in order to ensure adequate DNA collection.
- Lymphoid Malignancies Branch Clinical Research personnel will arrange for these samples to be delivered to Clinical Support Laboratory, Leidos Biomedical Research, Inc. in Frederick, MD for sample processing per established techniques maintained within standard operating procedures in the laboratory.

5.5 BIOMARKER AND RESEARCH METHODS

The technology platforms that are able to interrogate genomic structure and function are constantly in flux; therefore, the exact nature of the methodologies that will be employed will be assessed at the time that the samples are collected and ready for analysis. The protocol will be amended at that time, if needed, to describe the intended techniques prior to initiating the analyses.

Note: Platforms and procedures for analysis may be adjusted based upon current technology and/or collaborations in place at the time of actual analyses.

The following are technologies that are currently in use for each planned analysis:

5.5.1 Molecular Profiling

Immunohistochemical (IHC) analyses, including FISH and/or PCR testing, will take part in tumor tissue samples, including but not necessarily limited to CD2, CD3, CD4, CD5, CD7, CD8, CD14, CD16, CD20, CD25, CD38, CD45RA, CD45RO, CD56, CD62L, CD69, CD79a/CD79b, CD122, Foxp3, perforin, gamma/delta, CXCR3, CCR4, and NKG2D.

5.5.2 Immune Subset Analysis

Peripheral blood mononuclear cells (PBMC) will be assessed using multiparameter flow cytometry for immune subsets including but not necessarily limited to CD8+ T-cells, CD4+Foxp3- T-cells, Tregs, T_{ex}, Th1, Th2 and Th17+ CD4+ T-cells, NK cells and subsets, monocyte subsets, MDSC

subsets. Assessment may include functional markers, i.e. PD-1, Tim-3, CTLA-4, PD-L1, HLA-DR, Ki67 and/or CD40.

5.5.3 cfDNA/ctDNA

Since the methods of molecular monitoring in the peripheral blood is an emerging field with numerous technologies under development, the storage of peripheral blood mononuclear cells (PBMC), serum, and plasma will all be performed allowing for future comparison of the different compartments for analytes that include cell-free circulating tumor DNA (ctDNA), and RNA sequencing of circulating tumor cells. Studies to be performed on these samples include: cfDNA/ctDNA for liquid genotyping as a non-invasive dynamic monitoring of disease as well as monitoring for individual molecular aberrations that herald progression or disease transformation; specifically, amplification and sequencing of the VDJ segment of the immunoglobulin receptor is planned. Germline DNA obtained from saliva, blood, or buccal mucosa will be used to discriminate somatic from germline mutations during cfDNA and ctDNA analyses.

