1.1.3 Exploratory Objectives

- Evaluate changes in peripheral blood immune cell subsets and cytokine profiles, and correlation of these changes with clinical outcome.
- Evaluate changes in circulating tumor DNA to identify potential prognostic or predictive markers in patients with T-cell malignancies.
- Collect and store peripheral blood and other tissue samples for future correlative studies.

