2 ELIGIBILITY ASSESSMENT AND ENROLLMENT

2.1 ELIGIBILITY CRITERIA

2.1.1 Inclusion Criteria

2.1.1.1 Patients must have relapsed after or progressed during at least one line of prior systemic therapy (which may include allogeneic stem cell transplantation) for mature T or NK/T neoplasm, i.e. have relapsed and/or refractory mature T and NK neoplasm per 2016 WHO classification excluding chronic lymphoproliferative disorder of NK cells, aggressive NK-cell leukemia, and Cutaneous T-Cell Lymphoma.

2.1.1.2 T or NK/T neoplasm from initial diagnosis **or** recurrence must be histologically or cytologically proven and diagnosis be confirmed by the Laboratory of Pathology, NCI.

2.1.1.3 Patients with ALCL or CD30 positive MF/SS must have relapsed after or become intolerant to prior anti-CD30 targeting therapy treatment with brentuximab vedotin

2.1.1.4 For patients without circulating leukemia/lymphoma cells detectable by flow cytometry, a formalin fixed tissue block or 15 slides of tumor sample (archival or fresh) must be available at enrollment for performance of correlative studies. **NOTE:** Patients without circulating malignant cells must be willing to have a tumor biopsy if prior tissue or adequate archival tissue is not available (i.e., post-enrollment and prior to treatment).

2.1.1.5 Disease must be measurable with at least one measurable lesion by RECIL 2017 or mSWAT criteria (see Section [6.3](#)), or have an abnormal clonal T-cell population detectable by peripheral blood flow cytometry

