2.3.2.2 Laboratory Evaluations

NOTE: Results from outside NIH are accepted.

- CBC with differential, platelets and reticulocyte count
- Chemistry panels (as noted) or specific analyte required for eligibility, including: Creatinine (i.e., Acute Care Panel); serum calcium, phosphate, magnesium and albumin (i.e., Mineral Panel); ALT, AST, total bilirubin (i.e., Hepatic Panel, direct bilirubin if indicated); LDH
- Serum Lipase and Amylase
- Coagulation panel, including: PT/INR and a PTT
- Thyroid function tests, including: thyroid stimulating hormone (TSH) with reflex free thyroxine (T4)
- Hepatitis B surface antigen (HBsAg), Hepatitis B core antibody, Hepatitis C antibody (HCVAb) (qualitative), HIV 1/2 antibody (qualitative) and HTLV-1/2 serologies (within 3 months). **NOTE:** For individuals with a positive hepatitis B core antibody, HBV DNA PCR will be performed to screen for subclinical infection; for patients with

positive hepatitis C antibody, HCV PCR will be performed; for patients with positive HIV antibodies, HIV1/2 viral load will be checked.

- Urinalysis (with microscopic examination if abnormal)
- Serum or urine pregnancy test (B-HCG) for individuals of childbearing potential
- Clonal T-cell receptor rearrangement by PCR (peripheral blood and/or tissue), within 3 months prior to enrollment.

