10.4.8 Exploratory Analyses

The exploratory objectives such as seeking to identify potential biomarkers or T-cell clones in peripheral blood which are associated with response, will be assessed using descriptive statistics as well as non-parametric methods such as exact Wilcoxon rank sum tests. The analyses will be done without formal adjustment for multiple comparisons, but in the context of the number of tests performed.

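### The receptor-sequencing assay named for ctDNA targets the immunoglobulin receptor, although the trial enrols only T/NK neoplasms and its own clonality marker is the T-cell receptor

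*Combined protocol and SAP*

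**What the plan says.** The second exploratory objective (1.1.3) is to "Evaluate changes in circulating tumor DNA to identify potential prognostic or predictive markers in patients with T-cell malignancies". Section 5.5.3 describes the laboratory work behind it. It first plans "cfDNA/ctDNA for liquid genotyping as a non-invasive dynamic monitoring of disease", together with monitoring for individual molecular aberrations. It then adds, introduced by the word *specifically*, that "amplification and sequencing of the VDJ segment of the immunoglobulin receptor is planned". The closing sentence of the section says that germline DNA "will be used to discriminate somatic from germline mutations during cfDNA and ctDNA analyses".

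Elsewhere the protocol treats the disease and its clone as T-cell throughout:

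- Inclusion criterion 2.1.1.1 requires "relapsed and/or refractory mature T and NK neoplasm per 2016 WHO classification", with some entities excluded. No B-cell disease is eligible.
- The screening laboratory list (2.3.2.2) requires "Clonal T-cell receptor rearrangement by PCR (peripheral blood and/or tissue), within 3 months prior to enrollment".
- The exploratory analysis (10.4.8) describes the aim as "seeking to identify potential biomarkers or T-cell clones in peripheral blood which are associated with response".

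Section 5.5 says that methods will be settled when the samples are ready, that platforms and procedures may change, and that the protocol will be amended beforehand if needed.

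**The concern.** Clonotype tracking works by following the receptor rearrangement that marks the tumour clone. In this protocol that marker is the T-cell receptor. The only receptor assay named for ctDNA reads a different receptor, so the clone documented at screening is not linked to any planned ctDNA measurement.

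A laboratory following the text would profile immunoglobulin rearrangements in patients whose tumours are of T or NK origin. The resulting series would not be expected to rise and fall with tumour burden. Correlating it with response under 10.4.8 could then give a null or misleading result that says nothing about the regimen or the tumour. Plasma aliquots are also finite, so the target matters before they are used.

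**Working it through.** No sample size, power or error rate depends on this point, so the check is a comparison of the text.

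**Step 1: what each section takes as the clonal marker.**

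| Place | Material | Marker named |
|---|---|---|
| 2.1.1.5 Measurable disease | Peripheral blood, flow cytometry | Abnormal clonal T-cell population |
| 2.3.2.2 Screening | Blood and/or tissue, PCR | T-cell receptor |
| 10.4.8 Exploratory analysis | Peripheral blood | T-cell clones |
| 5.5.3 ctDNA | Cell-free DNA, sequencing | Immunoglobulin receptor |

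Section 5.5.3 stands alone. The protocol contains no T-cell receptor assay on cell-free DNA, and no B-cell question that would explain an immunoglobulin target.

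**Step 2: whether 5.5.3 plans any other ctDNA measurement.** It does. Liquid genotyping and monitoring of individual aberrations come before the receptor clause in the same sentence. The germline sentence that follows concerns somatic mutations, so it makes sense only if a mutation-based reading is also intended. Section 5.1.1 likewise plans germline sequencing to separate ctDNA from other cell-free DNA, and 5.7.1 expects ctDNA to be sequenced. None of this needs a receptor rearrangement.

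**Step 3: which samples are concerned.** In the table in 5.1.1 the ctDNA tubes are drawn on day 1 of cycle 1 and day 1 of cycles 2 to 6. That is 1 + 5 = 6 on-treatment draws for a participant who completes all cycles, plus each follow-up visit before progression. The former day -7 draw is retired with the lead-in window. Six is a maximum, because a footnote allows the ctDNA sample to be omitted when the research blood limit would be exceeded.

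**Step 4: which objectives are concerned.** Section 1.1.3 lists three exploratory objectives, and ctDNA is one of them. Only the receptor-based component of that one depends on the named target. The endpoints in 10.1 (MTD, adverse events, response, duration of response, PFS, EFS, OS) use no ctDNA result.

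**The case against.** The strongest reply is that nothing irreversible follows. Section 5.5 expects methods to be fixed later and provides for an amendment before the analyses start. Section 5.5.3 stores blood cells, serum and plasma, and 5.5.5 keeps leftovers. The target can therefore be changed without a new sample. This stands, and it removes most of the practical harm. It does not make the present text right: the clause permits a correction but does not make one, and nothing in it tells a laboratory that the stated target is wrong.

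A reader might go further and infer that the ctDNA objective would go unanswered. The documents do not support that, because mutation-based genotyping with matched germline DNA is planned alongside (step 2). It can be argued that *specifically* narrows the genotyping to the receptor assay, and that 5.5.3 gives no panel, depth or calling rule for ctDNA, since the thresholds in 5.5.4 are written for tumour samples. That makes the genotyping plan thin. It does not make it absent, and the germline sentence tells against the narrow reading.

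A reader might also infer that an immunoglobulin assay can never carry a signal in these tumours. The documents give no data on immunoglobulin rearrangement in T or NK neoplasms, so the claim has to stay at *would not be expected to*.

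**Conclusion.** The mismatch is real and is in the current text. Section 5.5.3 names a receptor target that disagrees with the eligibility criteria, the screening clonality test and the exploratory analysis plan, and no rationale is given.

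The consequence is limited to the clonotype-tracking part of one exploratory objective, and it arises only if the text is followed unamended. The rest of the ctDNA work, the banked samples and every primary and secondary endpoint are unaffected. Severity is minor.

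Two assumptions carry this conclusion. The first is the general premise that immunoglobulin rearrangement marks B-cell clones and is not the expected marker of a T-cell clone. The protocol does not state this, but its own choice of the T-cell receptor at screening is consistent with it. The second is that the mutation-based genotyping is a separate planned measurement, as the germline sentence indicates.

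**What to change.** Before any ctDNA assay is run, amend Section 5.5.3 as follows:

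1. Replace the immunoglobulin receptor with the T-cell receptor as the sequencing target, or state why an immunoglobulin target is wanted.
2. Tie the assay to the clone found by the screening T-cell receptor PCR. The protocol does not say that the screening test yields a sequence, so it should state how the clone is identified for tracking, for example from the baseline tumour or blood sample already required.
3. State that participants without a T-cell receptor clone, such as some with NK disease, will be followed by the mutation-based genotyping of cell-free DNA already planned.

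The cost is one phrase and one or two sentences in the next amendment. The blood tubes and time points stay the same, and there is no added burden on participants.

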5.5.4 DNA/RNA Sequencing

Genomic DNA and total RNA will be extracted from tumor samples using a Qiagen All-prep kit. For individual target genes that are recurrently mutated in T-cell malignancies, classical Sanger sequencing will be performed on PCR amplicons, using primers surrounding the known sites of mutation. To broadly assess mutations, next generation sequencing (e.g., on an Illumina HiSeq 2000 platform) will be employed, using a paired end sequencing strategy of libraries constructed from tumor DNA. DNA will either be sequenced in its entirety from a whole genome library or will be first enriched for exonic sequences using the Agilent Sure Select system, aiming for 30X or 100X average coverage per base, respectively. The sequence fragments will be mapped back to the genome using the BWA algorithm. Of sequences overlapping a particular base pair in the genome, the percent mutant calls greater than 20% with a minimum of 25X coverage will be considered as an arbitrary threshold for single nucleotide variants (SNVs). SNVs that are not present in the matched normal sample will be considered candidate somatic mutations.

A related technology, RNA-Seq, utilizes RNA from the tumor specimen to create a cDNA library for high-throughput sequencing. RNA-seq will be performed using Illumina kits followed by high-throughput sequencing on an Illumina HighSeq 2000 machine. The cutoffs for coverage and percent mutant calls mentioned above will also be used to identify putative SNVs. RNA sequencing will also be used to read out digital gene expression across the genome as described.

Recent advances in genomic technologies enable GEP at the single cell level, a distinct advantage over conventional GEP which cannot always distinguish tumor vs non-tumor gene expression. Single-cell approaches allow identification of the evolution of rare populations of resistant tumor cells, as well as identification of TME cells critical for the survival of the tumor. The Center for Cancer Research (CCR) has recently opened a single cell analysis core facility with expert staff headed by [name] within the CCR Genomics Core. This facility has the ability to take purified viably frozen cells banked from patient biopsies and prepare them, using well-validated 10X Genomics technology, for single-cell RNA sequencing. This core is directly integrated with the NCI Sequencing core facility to provide high-quality, deep-sequencing of the single cell RNA-SEQ samples, as well as ‘first-pass’ data processing and analysis. Data will then be transferred to lymphoma researchers and bio-informaticians for further analysis of gene expression patterns and cellular population dynamics.

5.5.5 Future Use

Any blood, tissue, or other products or portions leftover from other analyses will be stored for future research.

5.6 SAMPLE STORAGE, TRACKING, AND DISPOSITION

5.6.1 General

Samples will be ordered in CRIS and tracked through a Clinical Trial Data Management system. Should a CRIS screen not be available, the CRIS downtime procedures will be followed. Samples will not be sent outside NIH without appropriate approvals and/or agreements, if required.

5.7 SAMPLES FOR GENETIC/GENOMIC ANALYSIS

5.7.1 Description of the scope of genetic/genomic analysis

The research correlates for this study are expected to include DNA/RNA sequencing of tumors, including circulating tumor (ct) DNA. In addition, whole exome sequencing may include evaluation for known lymphoma mutations. For any genetic studies performed, the results will be deposited in a database such as dbGaP per NIH requirements. Although there is controlled access to such a database, such a submission carries theoretical risks of revealing the identity of the subject. This is discussed in the consent.

5.7.2 Description of how privacy and confidentiality of medical information/biological specimens will be maximized

Confidentiality for genetic samples will be maintained as described (Section [5.6](#)). In addition, a Certificate of Confidentiality has been obtained for this study.

5.7.3 Management of Results

Subjects will be contacted if a clinically actionable gene variant is discovered. Clinically actionable findings for this study are defined as disorders appearing in the American College of Medical Genetics and Genomics recommendations for the return of incidental findings that is current at the time of primary analysis.

5.7.4 Genetic Counseling

Subjects will be contacted at this time with a request to provide a sample to be sent to a CLIA certified laboratory. If the research findings are verified in the CLIA certified lab, the subject will be offered the opportunity to come to NIH to have genetic education and counseling to explain this result; at the time of any such event(s), these activities will be funded by the NCI/CCR in consideration of the specific circumstances. If the subject does not want to come to NIH, a referral to a local genetic healthcare provider will be provided (at their expense).

This is the only time during the course of the study that incidental findings will be returned. No interrogations regarding clinically actionable findings will be made after the primary analysis.

6 DATA COLLECTION AND EVALUATION

6.1 DATA COLLECTION

6.1.1 Summary

The PI will be responsible for overseeing entry of data into a 21 CFR Part 11-compliant data capture system provided by the NCI CCR and ensuring data accuracy, consistency and timeliness.

The principal investigator, associate investigators/research nurses and/or a contracted data manager will assist with the data management efforts. Primary and final analyzed data will have identifiers so that research data can be attributed to an individual human subject participant.

All adverse events (AEs), including clinically significant abnormal findings on laboratory evaluations, regardless of severity, will be followed until return to baseline or stabilization of event.

Document AEs from the first study intervention, Study Day 1 through 30 days after the last intervention. Beyond 30 days after the last intervention, only adverse events which are serious and related to the study intervention need to be recorded.

End of study procedures: Data will be stored according to HHS, FDA regulations, and NIH Intramural Records Retention Schedule as applicable.

Loss or destruction of data: Should we become aware that a major breach in our plan to protect subject confidentiality and trial data has occurred, this will be reported expeditiously per requirements in Section [7.2.1](#).

